## **5.17. Neutrophil Extracellular Traps (NETs) Analysis**

Recent evidence implicates neutrophil extracellular traps (NETs; a microbiocidal strategy characterized by externalization of nuclear and neutrophil granular material) in the pathogenesis of various autoimmune disease including lupus, rheumatoid arthritis and vasculitis. It has been proposed that NETs may serve as source of modified autoantigens and also promote targeted tissue damage. It is unknown if patients with inflammatory myopathies have enhanced NETosis and whether this phenomenon may play important role in the pathogenesis of these diseases. We will work in collaboration with [name] laboratory to evaluate this process in dermatomyositis patients and to evaluate the effect that sodium thiosulfate administration has on NETosis. Blood samples will be collected for evaluation to quantify neutrophil extracellular trap formation in the presence or absence of stimulation using fluorescent microscopy and/or sytox green.

## **5.18. Microparticle and Other Endothelial Biomarker Evaluation**

Endothelial microparticles (EMP) and platelet-derived microparticles (PDMP), which have been observed by others to be increased in small numbers of patients with lupus and dermatomyositis, will be assessed by flow cytometry in a 10-mL plasma citrate blood sample from patients using an LSR II digital flow cytometer, which provides higher sensitivity, resolution and faster rate of data acquisition. The features of LSR II are especially beneficial for rare event analysis, because EMP may represent less than 10% of total circulating MPs in the blood, and the machine may detect microparticles of smaller dimensions (100-200 nm). These will be correlated with established endothelial markers: Intercellular Adhesion Molecule – 1 (ICAM-1), vascular cell adhesion molecule (VCAM-1), E-selectin (CD62E), VE-cadherin (CD144), PECAM-1 (CD31), and others performed in the NIH Clinical Center laboratory, such as von Willebrand factor VIII related antigen and C-reactive protein levels. Monocyte-derived microparticles (CD14+), T lymphocyte-derived (CD3+) and B-lymphocyte-derived (CD19+), and platelet-derived microparticles (CD41), (CD61) will also be monitored. These studies may be performed on some of the patients enrolled in the protocol.

## **5.19. Center for Human Immunology (CHI) Assessments**

Samples will be collected for exploratory evaluations by the CHI for drug effects on the immune system using a series of techniques to attempt to clarify which immune parameters are perturbed in DM patients with calcification and how they change with treatment. Based on our experience with sodium thiosulfate we believe it is having a beneficial impact on patients' underlying myositis disease processes in addition to their calcinosis, and these studies will aid in better understanding the biologic causes for this observed clinical improvement. These assessments will include proteomics evaluation to assess changes in serum protein expression with drug treatment to evaluate which pathways may be altered by medication treatment. We will also evaluate this question at the RNA level. In addition, we will assess cytokines to determine if there is a decrease in signs of inflammation and what may be leading to that change. Cell surface marker and cell population changes may also provide insight into additional mechanisms of this medication so we will also evaluate changes in these areas. Blood samples will be collected at -10 and 0 weeks to establish a baseline value and variation in this population then again at weeks 2, 6, and 10 to evaluate for drug effect, and finally at weeks 24 and 62 to evaluate the longevity of any effect that was observed. Calcinosis

**Abbreviated Title:** Sodium Thiosulfate (STIC)

**Version Date:** July 07, 2023

samples that are aspirated will also be sent for cytokine analysis and flow cytometry to better understand the composition of liquefied calcinosis and its response to therapy.

## 5.20. Questionnaire Assessments

Quality of life questionnaires will be administered in this study as part of the participants' clinical care and for research purposes. Generally, parents, children and adult patients will complete these assessment tools. Details of tool administration by visit, including the individual(s) completing the assessment, are provided in Table 7 found in Appendix B.

We plan to administer the following quality of life assessments in this study:

- Child Health Questionnaire - Parent Form 50 (CHQ-PF50 for pediatric participants) or Medical Outcomes Study Short Form Health Survey (SF-36; for adult participants), which include a pain score as one of their components
- Childhood Health Assessment Questionnaire (CHAQ; for pediatric participants) or Health Assessment Questionnaire (HAQ; for adult participants), to capture activities of daily living functional assessments and a pain visual analog scale score (these are also part of the IMACS activity core set measures as noted in Section 5.21)
- Calcinosis Assessment Tool (CAT), which will assess calcinosis severity and change with time (as noted in Section 5.22)
- Mawdsley Calcinosis Questionnaire, which is an experimental tool for assessing calcinosis in scleroderma patients will also be used to try and capture information on calcinosis severity.
- Patient Reported Outcomes Measurement Information System (PROMIS®) questionnaire, which will be used to capture daily life functions and health-related quality of life
- Skindex-29, which will assess dermatology-related quality of life impairment

## 5.21. International Myositis Assessment and Clinical Studies (IMACS) Group Activity and Damage Core Set Measure Assessments

The IMACS forms will be completed by the patients, parents of the patients, and a physician in order to assess patients' disease throughout the study. Details of the timing of form administration are provided in Table 7 found in Appendix B.

The IMACS Disease Activity Core Set Measures and Damage Core Set Measures have been described by Rider *et al.*, (35), and are summarized on the IMACS website: <http://www.niehs.nih.gov/research/resources/imacs/>.

IMACS Disease Activity Core Set Measures include the following:

- Physician Global Activity - Visual Analogue Scale/Likert
- Patient/Parent Global Activity - Visual Analogue Scale/Likert
- Muscle Strength Testing - Manual Muscle Testing (MMT)

**Abbreviated Title:** Sodium Thiosulfate (STIC)

**Version Date:** July 07, 2023

- Functional Assessment Tools - Childhood Health Assessment Questionnaire (CHAQ; for pediatric participants), Health Assessment Questionnaire (HAQ; for adult participants), Childhood Myositis Assessment Scale (CMAS)
- Laboratory - Muscle Enzymes
- Extramuscular Assessment - Myositis Disease Activity Assessment Tool

The IMACS Damage Core Set Measures include the following:

- Myositis Damage Index (MDI)
- Physician Global Assessment of Disease Damage
- Patient/Parent Global Assessment of Disease Damage
- Muscle Strength Testing – MMT (also part of the Disease Activity Core Set Measures, as listed above)
- Functional Assessment Tools - HAQ, CHAQ (also part of the Disease Activity Core Set Measures, as listed above)

## **5.22. Calcinosis Assessment Tool (CAT)**

The CAT is a new tool our group has developed that we will be using to assess calcinosis severity and change with time, with the goal of validating this tool as part of this study. These questionnaires will involve a short form completed by the participant and the parent of a juvenile patient. The CAT also includes a pain VAS. Details of the timing of form administration are provided in Table 7 found in Appendix B.

## **5.23. Cutaneous Dermatomyositis Disease Area and Severity Index (CDASI)**

The CDASI is a physician completed assessment of cutaneous disease in dermatomyositis. We will administer the CDASI version 2 to patients at specific time points as described in Appendix B Table 5. Whenever possible, these measurements will be performed by the same clinician throughout the trial.

## **5.24. Durometry**

Durometry will be performed on patients. At least three separate areas of calcinosis will be evaluated during each assessment and the same area will be evaluated across different points in the study. The durometer small cylinder with a tiny mobile bump at the measuring end called the footpad. During an assessment, the evaluator will place the footpad at an angle to the calcinosis lesion and then roll it into a perpendicular orientation to the calcinosis lesion and press it firmly for several seconds. This will be performed 3 times at each site evaluated and the results averaged to provide a reading for that site. The schedule for durometry measurements is as described in Appendix B Table 4. Whenever possible, these measurements will be performed by the same clinician throughout the trial. They will be done using an OO digital DD-4 rex gauge digital durometer model number digital DD-4-OO. These will be recorded on the Calcinosis Sentinel Lesion Form along with additional physical exam comments on these areas of calcinosis.

**Abbreviated Title:** Sodium Thiosulfate (STIC)

**Version Date:** July 07, 2023

## 5.25. CT/PET

Due to technical issues the MRI/PET machine may not be available for obtaining protocol described MRI/PET studies. CT/PET is an additional method of collecting this PET data although it involves additional radiation over that of MRI/PET. We will perform a CT/PET from the base of the skull to the toes. All participants receiving a CT/PET will receive a brief medical history to determine if they have any condition that would preclude a CT/PET. These contraindications include, but are not limited to, pregnancy, uncontrolled diabetes or age older than 95 years. A history of radiation exposure will be taken prior to enrollment and prior to performing any research study involving ionizing radiation. If the patient has received more than 0.5 rem for research purposes in the past 12 months prior to enrollment, we will delay enrollment until their time 0 would be 12 months or more from their last research radiation exposure. If the patient is already enrolled in the study and they have received more than 0.5 rem for research purposes outside of this protocol, we will review their situation with the DSMB and the IRB to decide whether to continue with currently planned research assessments involving radiation or to alter such assessments. All female subjects will receive a pregnancy test prior to this study and will be excluded from this testing if they are pregnant. All patients will have their blood sugar checked immediately prior to the study to ensure it is below 200 mg/dl, because hyperglycemia interferes with the uptake of radioactive glucose required for the PET scan. If blood glucose is found to be elevated, the medical team will work to safely lower the blood sugar and reassess if the blood sugar is at a level where the scan results would be interpretable. Prior to undergoing the scan, all subjects or their parents/guardians will complete a standard radiology questionnaire that determines other potential risks of the procedure that may have previously been missed. Prior to the scan patients will receive a detailed instruction sheet explaining that they need to minimize exercise for 48 hours prior to the scan, consume a high fat diet for 24 hours prior to the scan, and fast for 6 hours prior to the scan.

## 6. Collection and Storage of Human Specimens or Data

We will collect and store clinical and laboratory data and biologic specimens on all participants. Long-term storage of all biological specimens in repositories will be coordinated by [name] laboratory by dividing specimens between her laboratory facilities and NIEHS storage facilities for redundancy.

Privacy/confidentiality will be protected by: labeling all data and samples with a code; limiting distribution only to IRB-approved collaborators; limiting all data sharing procedures to only those conducted through encrypted electronic files or secure fax machines; and by keeping all data in restricted areas and locked filing cabinets, and by keeping all samples in restricted areas.

Retention of coded data and samples is needed until the end of the study to allow reassessment of information or assays as required to assist in the interpretation of individual outcomes and the overall results of the protocol.

Materials remaining after the planned analyses will stay in repositories, coded and identifiable only to the investigators intimately involved in the conduct and analysis of the study. To complete the studies described in the protocol, subjects' biologic samples coded with numbers only may be sent to collaborators, and samples will only be identifiable to those with restricted access to the database. Fully anonymous repository samples may be used for future research studies involving identification of autoimmunity-related genes or other markers that may help in improving understanding of the diagnosis, prognosis or pathogenesis of autoimmune disorders or for other research use beyond the scope of this study if subjects have agreed to that in the consents they have signed. If patients have not signed consent for anonymous research use beyond the scope of this study, we will seek appropriate IRB approval.

All data and any remaining materials will be returned to the PI at the completion of the study. All biological specimens will be frozen and stored in EAG laboratory freezers and/or in the NIEHS repository for research purposes as outlined in this protocol for as long as the protocol is active. We will track all collected data and specimens using local secure databases. When the protocol is closed all data and samples will be transferred to an appropriate long term data storage protocol.

Any loss or unanticipated destruction of samples or data (e.g., malfunction of a freezer) will be reported to the IRB. Additionally, a participant may decide at any point not to have their samples stored. In this case, the PI will destroy all known remaining samples and report this action to both the participant and to the IRB.

## **8. Study Statistical Considerations and Analytic Plan**

### **8.1. Statistical Analyses**

A single-arm, open-label study is proposed to evaluate the primary hypothesis that participants treated with sodium thiosulfate will experience greater improvement in calcinosis activity as assessed by a change in the calcinosis visual analogue scale (VAS) after treatment compared with any change in calcinosis activity visual analogue scale during the observation period prior to treatment with sodium thiosulfate.

A intention-to-treat statistical analysis will be performed where first, the primary outcome, the change in calcinosis activity VAS score from Week 0 to Week 10 compared with any change in calcinosis activity VAS score observed during the pre-treatment period (from Week -10 to Week 0), will be analyzed using a two-tailed paired t-test. This will be reported as absolute change for the primary outcome and calculated by taking value of the time 0 score minus the time -10 score and subtracting from that the value of the time

**Abbreviated Title:** Sodium Thiosulfate (STIC)

**Version Date:** July 07, 2023

10 score minus the time 0 score. As secondary end points, we will also evaluate any changes as relative percent change and absolute percent change. Second, two-tailed paired t-tests will be performed to test for significant differences in the primary outcome for the adult and juvenile dermatomyositis patients separately. Multiple testing adjustments will be used to control for the multiple comparisons on the VAS score outcomes for the subgroup analysis.

Two-sided paired t-tests will be performed to test for significant differences in the relative percent change in VAS score, absolute percent change in VAS score, and the secondary outcome of change in quality of life score (Physical Function Score of CHQ-PF50 for children, SF-36 for adults) from Week 0 to Week 10, compared with any change in quality of life score observed during the pre-treatment period (from Week -10 to Week 0). The secondary outcomes of changes in the components of quality of life over time, changes in functional disability over time, change in muscle strength over time, and changes in gene expression associated with therapy will also be analyzed using paired t-tests. For the gene expression analysis, multiple testing adjustments will be used to control the false discovery rate. Categorical measures of improvement in calcinosis lesions, improvement in or stabilization of myositis activity, and incidence of adverse events will be analyzed using McNemar tests. Fisher exact tests will be used to test for differences between responders and non-responders to therapy. The severity of adverse events and quantitative measures of improvement in calcinosis lesions and myositis activity will be analyzed using paired t-test or regression to control for additional covariates. Generalized linear mixed models will be considered to analyze quantitative secondary outcomes across time. Descriptive statistics, such as mean, median and standard deviation, of the primary outcome and secondary outcomes of change in VAS, change in quality of life (QOL), change in functional disability, improvement in calcinosis lesions, and change in muscle strength are also of interest and will be used to plan further studies. Prior to statistical testing, the normality of quantitative measures will be evaluated by plotting the empirical distributions of the quantitative measures to look for deviations from normality as well as using QQ-plots. For non-normally distributed endpoints, normalizing transformations, such as the log transformation, will be applied. If normality cannot be achieved by transforming the data, analogous nonparametric tests, such as the Wilcoxon Signed Rank test, will be used in the analysis. The multiple comparison adjustment method that will be used is a stepwise Bonferroni-Class Method as published in Holm (39) and Hochberg (40).

The validity of the calcinosis assessment tool (CAT) will be assessed by focusing on the similarity between the CAT and other disease activity measures, like the Global Physician Score (GPhS) and Patient Reported Outcomes Measurement Information System (PROMIS®). Large disagreement between the CAT and other disease activity measures would suggest that the CAT tool is not measuring improvement in calcinosis but small differences may indicate that the CAT is capturing improvement in calcinosis that the other measures are not capturing. To assess the similarity between the disease activity measures, the Spearman rank correlation coefficient between the change in the CAT responses and the change in the other disease activity measure responses will be calculated. One can then test whether this correlation coefficient is different than zero, which would suggest an association between the two measures. A kappa statistic will be calculated to assess the agreement between discrete measures in the CAT and other discrete measures of disease activity. In the case where the number of categories observed by the CAT and other discrete measures of numbers of categories differ, the comparison will be accomplished by comparing the pooled scores for all categories of

**Abbreviated Title:** Sodium Thiosulfate (STIC)

**Version Date:** July 07, 2023

the CAT to the pooled scores of each independent finding using a nonparametric Wilcoxon ranked sum statistic. Evaluation of the Mawdsley Calcinosis Questionnaire will be performed in the same manner as for the CAT. A cluster analysis will be considered to explore how well the change in VAS, along with other measures of disease activity, such as change in Global Physician Score, Patient Reported Outcomes Measurement Information System, MRI, CT scans, DEXA scans and vascular imaging, can distinguish between responders to intravenous sodium thiosulfate therapy and non-responders. Responders will be defined as those individuals who meet the primary end point and non-responders will be those individuals who fail to meet the primary end point. A Spearman rank correlation coefficient will be used to identify disease activity measures that are highly correlated and contain the duplicate information. This will aid in variable selection for future multivariate analyses to identify responders to therapy. We will also attempt to assess the responsiveness of these tools through their standardized response means.

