## 8.2. Sample Size Considerations

Sample size estimates for this analysis are based on the following assumptions:

1. The primary outcome is the mean difference in the change in calcinosis activity during the pre-treatment period and the change in calcinosis activity during the treatment period.
2. The calcinosis activity will be measured by the calcinosis visual analogue scale (VAS) score. This score ranges from 0 to 100 mm.
3. Pre-treatment period change in calcinosis activity is calculated by subtracting the calcinosis VAS score at Week -10 from the calcinosis VAS score at Week 0. Treatment period change in calcinosis activity is calculated by subtracting the calcinosis VAS score at Week 0 from the calcinosis VAS score at Week 10.
4. The treatment period change in calcinosis activity subtracted from the pre-treatment period change in calcinosis activity is approximately normally distributed or can be transformed such that it will be approximately normally distributed.
5. The sample size estimate is the sample size required after attrition.

There are few prior data on the use of sodium thiosulfate for treatment of the calcinosis comorbidity in dermatomyositis patients. Therefore, there is limited information to estimate the necessary sample size to achieve adequate power. For the power analysis, a standard deviation ranging between 5 and 20 mm is assumed for the difference in the change in calcinosis activity between the treatment and pre-treatment periods based on previous studies that use visual analog scale measurements (Kelly 2001 and Demoly et al. 2013). The power analysis is based on two-sided, paired t-tests with a within subject correlation of 0.5 and 90% power. The sample sizes required for a range of significance levels, assumed standard deviations, and mean differences in the change in calcinosis activity VAS score between the pre-treatment and treatment period are given in Table 3.

**Table 3 Sample Sizes required, after attrition, to detect significant differences in the change in calcinosis activity between the pre-treatment and treatment periods. The estimates are based on two-sided, paired t-tests and 90% power where  $\alpha$**

**Abbreviated Title:** Sodium Thiosulfate (STIC)

**Version Date:** July 07, 2023

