**denotes the significance level and  $sd$  denotes the standard deviation of the differencesa.**

Mean Difference b	$\alpha=0.025$				$\alpha=0.05$			
	$sd=5$	$sd=10$	$sd=15$	$sd=20$	$sd=5$	$sd=10$	$sd=15$	$sd=20$
10	6	16	31	53	5	13	26	44
11	6	13	26	44	5	11	22	37
12	5	12	23	38	5	10	19	32
13	5	11	20	32	4	9	17	27
14	5	10	17	28	4	8	15	24
15	5	9	16	25	4	7	13	21
16	4	8	14	23	4	7	12	19
17	4	8	13	20	4	6	11	17
18	4	7	12	18	4	6	10	16
19	4	7	11	17	4	6	9	14
20	4	6	10	16	3	5	9	13
25	4	5	8	11	3	5	7	9
30	3	5	6	9	3	4	5	7

aIn between-patient standard deviation of the differences in change in calcinosis activity score between the treatment and pre-treatment periods

[figure not shown]
bThe mean of the differences in change in calcinosis activity between the treatment and pre-treatment periods

Assuming a standard deviation of 10 and a significance level of 0.05, a sample size of 13, after attrition, will provide at least 90% power to detect an improvement in calcinosis VAS score between the treatment and pre-treatment periods of at least 10 mm. If the standard deviation is 15, then a sample size of 13 will detect a mean difference of at least 15 mm. The sample size required depends on the assumed within subject correlation. Figure 2 illustrates how the required sample size will change depending on the assumed within subject correlation. Generally, the larger the assumed within subject correlation, the smaller the required sample size. For the subgroup analysis focusing on the juvenile and adult DM patients separately, a Bonferroni correction can be used to control the overall family-wise error rate to below 0.05 giving a significance level of  $0.05/2=0.025$  for each paired t-test in the subgroup analysis. Assuming that approximately the same number of juvenile and adult DM participants is enrolled in the study, a sample size of 13 for the combined group will result in at least 6 participants in each age subgroup. Assuming subgroup sizes of 6 and a standard deviation of 10, there will be at least 90% power to detect age group specific mean differences of at least 20 mm.

**Abbreviated Title:** Sodium Thiosulfate (STIC)

**Version Date:** July 07, 2023

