### 8.3. Accrual Number

Based on the information provided in preliminary data, unpublished reports, other studies involving sodium thiosulfate therapy, and the power analysis, the targeted number of participants to complete this study is 13. Considering the involved schedule of this therapy balanced with the lack of alternative treatment options for these patients, we anticipate a dropout rate of approximately 25%. Thus, to achieve a final sample size of 13 participants completing the study, we plan to enroll 18 participants. As discussed initially completers will be patients who receive all infusions or who reach the primary end point by week 6. For patients who need medication escalation prior to week 10 we will attempt to enroll another patient to use for the primary analysis instead of them as long as the total enrollment is still 18 or less patients.

Based on our experience enrolling a similar population, we anticipate screening approximately 5-6 individuals for every 1 eligible participant. Thus, we anticipate screening approximately 100 individuals for this study. Screening will be done by phone or in person interview and review of medical records. If the patient has been involved in other research studies information from those studies may also be considered.

**Abbreviated Title:** Sodium Thiosulfate (STIC)

**Version Date:** July 07, 2023

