**Table 7 Schedule of Quality of Life and Myositis Assessments by Study Week**

Assessment	Completed By...	Screening	-10	-4	0	2	4	6	8	10	24	62
CHQ-PF50 (if pediatric) or SF-36 (if adult)	Patient AND Parent of participant (for CHQ); Participant (for SF-36)		X	X	X	X	X	X	X	X	X	X
Physician Calcinosis Visual Analogue Scale	MD	X	X		X	X	X	X	X	X	X	X
Calcinosis Type and Extent Form	MD	X(optional)	X		X			X		X	X	X
Calcinosis Sentinel Lesion Form	MD		X		X			X		X	X	X
IMACS Activity Core Set Measures:												
Physician Global Activity	MD	X	X		X	X	X	X	X	X	X	X
Patient/Parent Global Activity	Participant and parent of participant	X	X	X	X	X	X	X	X	X	X	X
CHAQ (if pediatric) or HAQ (if adult),	Parent of participant and pediatric participant (for CHAQ); Participant (for HAQ)	X	X	X	X	X	X	X	X	X	X	X
Childhood Myositis Assessment Scale (CMAS)	MD	X (optional)	X		X	X	X	X	X	X	X	X
Myositis Disease Activity Assessment Tool (MDAAT)	MD	X	X		X	X	X	X	X	X	X	X
IMACS Disease Damage Core Set Measures:												
Myositis Damage Index (MDI)	MD		X		X	X	X	X	X	X	X	X
Physician Global Assessment of Disease Damage	MD	X	X		X			X		X	X	X
Patient/Parent Global Assessment of Disease Damage	Participant and parent of participant		X	X	X			X		X	X	X

**Abbreviated Title:** Sodium Thiosulfate (STIC)

**Version Date:** July 07, 2023

Assessment	Completed By...	Screening	-10	-4	0	2	4	6	8	10	24	62
IMACS Assessment of Study Outcome Form	MD, Participant, and parent of participant			X a,b	X b			X		X	X	X
Disease Activity Score (DAS)	MD		X		X	X	X	X	X	X	X	X
Calcinosis Assessment Tool (CAT), including Pain VAS	Participant and parent of participant, reviewed by MD, MD	X	X	X a	X	X	X	X	X	X	X	X
Mawdsley Calcinosis Questionnaire	Participant and parent of participant, reviewed by MD, MD		X	X a	X	X	X	X	X	X	X	X
PROMIS® Questionnaire	Participant and parent of participant (pediatric pts)		X	X a	X	X	X	X	X	X	X	X
Skindex-29+3	Participant and parent of participant (pediatric pts)		X	X	X	X	X	X	X	X	X	X
Adult Myopathy Assessment Tool (AMAT)	Rehab Medicine Department		X		X			X		X	X	X
Motor Function Measurement (MFM)	Rehab Medicine Department		X		X			X		X	X	X
Functional Index 3 (FI3)	Rehab [name]		X		X	X	X	X	X	X	X	X
Passive Range of Motion (ROM)	Rehab Medicine Department		X									
Targeted Passive Range of Motion	Rehab Medicine Department				X	X	X	X	X	X	X	X

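### The primary analysis is labelled intention-to-treat but needs a Week 10 score, has no rule for a missing one and leaves the Week 2 to 8 VAS unused, so response-related loss could bias it

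*Combined protocol and SAP*

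**What the plan says.** Section 8.1 opens the primary analysis with "A intention-to-treat statistical analysis will be performed where first, the primary outcome", defined as the Week -10 to Week 0 change minus the Week 0 to Week 10 change, which "will be analyzed using a two-tailed paired t-test". No analysis set is defined. Section 8 contains no imputation, no missing-data rule and no missing-data sensitivity analysis.

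Section 8.2 sizes the trial on patients remaining: "Assuming a standard deviation of 10 and a significance level of 0.05, a sample size of 13, after attrition", gives at least 90% power for 10 mm. Section 8.3 adds "we anticipate a dropout rate of approximately 25" per cent and enrols 18 to obtain 13 completers. A completer there is someone who receives all infusions or reaches the primary end point by Week 6.

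Table 7 in Appendix B schedules the "Physician Calcinosis Visual Analogue Scale" at screening and at Weeks -10, 0, 2, 4, 6, 8, 10, 24 and 62. Longitudinal models appear once in Section 8.1, for other endpoints: "Generalized linear mixed models will be considered to analyze quantitative secondary outcomes across time".

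Four further provisions matter:

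- Section 3.1 keeps patients withdrawn for a serious adverse event in the assessment schedule. It tries to keep other withdrawals in it too, and brings the Week 6 or 10 assessment forward for those known in advance to be unable to return.
- Section 14.2 has withdrawn patients return for assessments as far as tolerated and safe.
- Section 4.1, repeated in 8.3, replaces a patient who exceeds the medication limits before Week 10 in the primary analysis if an added patient completes treatment. A secondary analysis of all patients is promised.
- Section 5.5 does not count a patient found pregnant before Week 10 as a completer for the primary outcome.

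**The concern.** The label and the method do not match. A paired t-test on a three-visit contrast has nothing to enter for a patient without a Week 10 score, so in practice it analyses the patients who have one. Sizing on patients after attrition points the same way. The replacement and pregnancy rules then remove patients because of events after enrolment, which intention-to-treat is meant to prevent.

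With one arm, no control group shares the same loss. If patients doing badly by Week 4 or 6 are the ones who do not return, the remaining mean change looks better than the drug's effect. At the planned size the loss of a few patients can move the estimate by an appreciable part of the 10 mm design difference. Scores that would show how leavers were doing are already scheduled, but the primary analysis does not use them.

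**Working it through.** **The plan's own figures.** Let D = (W0 − W−10) − (W10 − W0), positive for benefit. With mean difference 10, SD 10, two-sided alpha 0.05 and n = 13, the noncentrality is 10/(10/√13) = 3.61 on 12 df. The exact noncentral t gives power 0.911, so 13 reproduces. Enrolment is 13/0.75 = 17.3, rounded up to 18, which also reproduces. Losing 5 of 18 is 27.8%. If all 18 were analysed, power would be 0.979.

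**How far loss can move the result.** Take 18 enrolled, 5 lost, 13 analysed, SD(D) = 10 and no drug effect. Let the tendency to leave correlate with a poor value of D (assumed; the documents give no figure):

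| Correlation | Bias towards benefit | Two-sided type I error |
|---|---|---|
| 0 | 0 mm | 5.0% |
| 0.3 | 1.3 mm | 7.7% |
| 0.5 | 2.2 mm | 13% |
| 0.7 | 3.1 mm | 23% |
| 1.0 (worst case) | 4.4 mm | 52% |

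Bias in mm scales with the SD: the worst case is 2.2 mm at SD 5 and 8.9 mm at SD 20, the ends of the range in Section 8.2. If good responders left instead, the sign would reverse.

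**A more moderate mechanism.** Assumptions, none of them from the documents: VAS = patient intercept (SD 12) + linear on-treatment response (SD 6.8 by Week 10) + visit noise (SD 3). Since D = 2·W0 − W−10 − W10, Var(D) = 6.8² + 6 × 3² = 46.2 + 54 = 100.2, so SD(D) = 10.0. About 25% leave after Week 4, with log-odds rising by about 1 per SD of poor Week 0 to 4 change. With no drug effect, the t-test on patients with a Week 10 score gives:

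| Leavers assessed at Week 10 | Bias | Type I error |
|---|---|---|
| None | about 1.6 mm | about 9% (8.3 to 9.2% across repeat runs) |
| Half | about 0.7 mm | about 6% |
| Three quarters | about 0.3 mm | about 5% |
| None, but half of the loss before dosing | about 0.9 mm | 6.6% |
| None, loss unrelated to response | 0 mm | about 5% |

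With a response SD of 9 and noise SD of 4, SD(D) = √(81 + 96) = 13.3. With no leaver assessed, the bias is then 2.1 mm and the type I error 8.6%.

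**The same data with all visits used.** In the SD 10 case with no leaver assessed, a REML model with random intercept and on-treatment slope shows 0.0 mm and 4.9% (800 replicates). With a true 10 mm effect it returns 10.1 mm, against 11.7 mm from the t-test. The data were generated from that model, so good performance there is expected. A small check (100 replicates) with categorical visits and a non-linear response also stayed near zero bias.

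**The case against.** The strongest case against starts with the 25%. A reader might infer that the plan discards a quarter of its patients for want of a Week 10 score. The documents do not say so. Dropout in Section 8.3 is counted against completion of treatment, and a patient who stops infusions may still be assessed at Week 10 under Sections 3.1 and 14.2. Rapid responders who stop at Week 6 are also brought back. Nor does any written rule drop patients without a Week 10 score; exclusion follows from the form of the test and from the plan's silence. This objection stands.

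The brought-forward assessment also helps. In a harsher scenario, where the 5 patients with the worst Week 4 or 6 change all leave, completers alone show 2.7 to 4.0 mm of false benefit. Using the last on-study score as Week 10 cuts this to between −0.6 and +1.0 mm. But Section 8 never says whether such a score counts as Week 10, and the rule covers only non-medical or voluntary withdrawals known in advance.

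A reader might also infer that any loss will appear as drug benefit. That is not established. Lack of response is not a listed withdrawal criterion in Section 14.2, and Section 8.3 notes that these patients have few alternatives, which gives non-improvers a reason to stay. The direction is plausible, since good responders are deliberately retained, but it is conditional.

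Finally, a three-visit paired t-test is a conventional choice, and a mixed model for 18 patients carries assumptions of its own. Both points are fair. They argue for a parsimonious model and for keeping the t-test as support, not for leaving missing data unaddressed.

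**Conclusion.** The point holds in conditional form. The plan claims intention-to-treat but specifies a test that can use only patients with all three scores. It has no rule for a missing Week 10 score, ignores four scheduled on-treatment VAS visits, and removes some patients by rule.

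The likely size is moderate: with SD 10 and no drug effect, about 0.7 mm and 6% type I error if half of the leavers are assessed, and about 1.6 mm and 9% if none are, against a design difference of 10 mm. These figures assume loss after Week 4 that depends on poor early response. The bias vanishes if loss is unrelated to response, and neither its direction nor a 25% rate of missing Week 10 scores can be read from the documents. The change should be made, but the point does not by itself invalidate the trial.

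**What to change.** 1. Keep the contrast (W0 − W−10) − (W10 − W0). Estimate it in all dosed patients by a REML repeated-measures mixed model with categorical visits, using the VAS at Weeks -10, 0, 2, 4, 6, 8 and 10 and a small-sample degrees-of-freedom correction.
2. Pre-specify a parsimonious covariance, for example random intercept plus on-treatment slope. An unstructured matrix over seven visits has 7 × 8/2 = 28 parameters, too many for 18 patients.
3. Enter a brought-forward Week 10 assessment at the time it was made, not as Week 10.
4. Keep the paired t-test as supportive. With complete data and an unstructured three-visit model, the two estimates coincide.
5. Add a missing-not-at-random sensitivity analysis, for example shifting unobserved Week 10 scores by increasing amounts until the conclusion changes.
6. Include in the primary set the dosed patients removed by the replacement rule (Sections 4.1 and 8.3) and the pregnancy rule (Section 5.5), or drop the intention-to-treat label. The mixed model does not settle this by itself.

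The cost is analysis-plan wording; no visit or measurement is added. The downsides are that a covariance model must be chosen for 18 patients and that validity rests on missing at random. Patients lost before dosing are not recovered by either method.
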